8.2.2. Underlying Malignancy Diagnosis

1. Malignancy type (R/R AML, untreated AML, MDS, or other).
2. If R/R AML, prior history of MDS (yes or no).
3. WHO classification of AML.
4. Time (month) from the initial diagnosis, calculated from time of initial diagnosis to date of first dose.

A by-subject listing of malignancy type will also be provided.

8.3. Medical/Surgical History and Concomitant Disease

Medical and surgical history, as well as concomitant disease, will be summarized by the Medical Dictionary for Regulatory Activities (MedDRA) version 20.0 by system organ class (SOC) and preferred term (PT). The summary will be produced for Phase 1 dose escalation, Part 1 Expansion, the combined Phase 1, Phase 2, and the combined Phase 1/2 in FAS. Prior medical/history is defined as medical condition with a start date prior to start of study treatment. Concomitant disease is defined as an active disease that ended on or after the start of study treatment. They will be summarized separately.

8.4. Prior, Concomitant, and Post-Treatment Medications/Procedures

[REDACTED]

8.4.1. Prior/Concomitant/Post-treatment Medications

[REDACTED]

8.4.2. Concomitant/Post-Treatment Procedures

All concomitant/post-treatment procedures will be summarized in frequency tabulations (subject counts and percentages) and by SOC and PT.

[REDACTED]

8.4.3. Prior/Post-treatment Therapies for the Underlying Malignancy

This section includes therapies for the underlying malignancy including surgery, radiation, systemic or any other therapy, regardless of discontinuation date of treatment. In addition to the analyses elaborated below, listings for prior and post-treatment therapies for the underlying malignancy will be linked through a roadmap for each subject to facilitate subject-level review.

8.4.3.1. Surgeries

Post-treatment surgeries as documented on the designated CRF pages will be produced by SOC and PT and summarized in frequency tabulations.

A listing will be provided for post-treatment surgeries.

8.4.3.2. Radiation

The number and percentage of subjects who had any prior/post radiation therapy will be presented, if available. Summaries will include total frequency of subjects receiving any prior/post radiation therapy. For subjects with radiation therapy, treatment site, start/stop date, and dose will be presented in a listing.

8.4.3.3. Systemic Medication for the Underlying Disease

The number and percentage of subjects with any prior/post systemic medication for the underlying malignancy will be presented by ATC Classification. For subjects with systemic medication for the underlying malignancy, detailed information will be presented in a listing.

8.4.3.4. Stem Cell Transplants

The number and percentage of subjects with any on study stem cell transplants will be presented. Transplant by IDH2 mutation will be analyzed in the combined Phase 1, Phase 2, and the combined Phase 1/2 R/R AML subjects.

For subjects with stem cell transplants, type and date of procedure will be presented in a listing.

9. STUDY TREATMENTS AND EXTENT OF EXPOSURE

Descriptive statistics will be used to summarize treatment duration, duration of treatment exposure, cumulative dose, average daily dose, dose intensity, relative dose intensity and dose modification. These analyses will be presented by subject groups as described in items 1 to 5 of [Section 5.1](#) for the SAS. Tables will also be provided for Phase 1 dose escalation by assigned dose groups in the DDS.

Cycle duration is defined as the period from Day 1 of each cycle to one day prior to the Day 1 of the subsequent cycle; for the last cycle, the end date is the date of last dose.

For subjects who discontinued from study treatment but restarted AG-221, the data after restarting AG-221 will not be used for analysis in this section, however, will be presented separately in listings.

9.1. Treatment Duration and Exposure

Duration of treatment (months) is defined as: $(\text{treatment end date} - \text{treatment start date} + 1) / 30.4$. The treatment start date is the date of the first dose of study drug, and the treatment end date is the last dose date. For subjects who are still on treatment at a data cut-off date, treatment end date will be the earlier date of data cut-off date and last day that the subjects take study drug.

Duration of treatment exposure (months) is defined as: $(\text{Treatment end date} - \text{treatment start date} + 28) / 30.4$. If death date is after treatment end date and earlier than 28 days after treatment end date, duration of treatment exposure is defined as: $(\text{Death date} - \text{treatment start date} + 1) / 30.4$.

Treatment duration and exposure will be summarized by investigator assessed best response for the combined Phase 1, Phase 2, and the combined Phase 1/2 R/R AML subjects and overall.

A subject data listing of study drug records will be provided.

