5. GENERAL STATISTICAL CONSIDERATIONS

5.1. Reporting Conventions

Tabulations will be produced for subject disposition, demographic and baseline disease characteristics, safety, and clinical activity parameters. The study data will be analyzed and reported for efficacy/safety when applicable based on all subjects' data from the Phase 1 dose escalation, the Part 1 Expansion, the combined Phase 1, Phase 2, and the combined Phase 1/2 up to the data cut-off date of 29 July 2019.

Unless specified otherwise, the data will be presented as specified below:

1. In Phase 1 dose escalation, all subjects (combining different malignancy types [overall]) will be utilized. Data will be summarized by total daily dose groups, unless otherwise specified. The total daily dose is defined as the total dose a subject receives during a day based on the assigned or actual dose regimens for efficacy and safety, respectively.
2. In Part 1 Expansion, all subjects (combining different malignancy types) will be utilized and will be grouped into 4 arms (groups):
 - Arm 1: R/R AML and age ≥ 60 years, or any subject with AML regardless of age who has relapsed following a BMT.
 - Arm 2: R/R AML and age < 60 years, excluding subjects with AML who have relapsed following a BMT.
 - Arm 3: Untreated AML and age ≥ 60 years that decline standard of care chemotherapy.
 - Arm 4: IDH2-mutated advanced hematologic malignancies not eligible for Arms 1 to 3.
3. In the combined Phase 1, analyses will be presented by total daily dose groups as < 100 mg, 100 mg and > 100 mg for subjects with R/R AML. The overall subjects in the combined Phase 1 will be summarized by malignancy type including R/R AML, untreated AML, MDS, and other.
4. In Phase 2, data will be summarized primarily for all R/R AML subjects.
5. In the combined Phase 1/2, R/R AML will be presented by total daily dose groups as < 100 mg, 100 mg and > 100 mg, and the overall subjects will be presented by malignancy type.

For subjects who were discontinued from study treatment, underwent HSCT, and then re-started AG-221, data after restarting AG-221 will be excluded from all summary analyses except for death. The data collected after restarting AG-221 will be provided in listings.

Categorical variables will be summarized by frequency distributions (number and percentages of subjects) and continuous variables will be summarized by descriptive statistics (number of subjects, mean, standard deviation (SD), median, minimum, and maximum).

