11.1. Adverse Events

Adverse events will be analyzed in terms of treatment-emergent adverse events (TEAEs), which are defined as any AEs that begin or worsen on or after the start of study drug through 28 days after the last dose of study drug. All AEs will be coded using MedDRA version 20.0. The severity will be graded based on NCI CTCAE version 4.03.

A treatment-related TEAE is defined as TEAE that is suspected (possibly or probably related) by the Investigator to be related to the study drug. The incidence of TEAEs will be summarized by MedDRA SOC and PT. The intensity of AEs will be graded 1 to 5 according to the NCI CTCAE version 4.03. For all other AEs not described in the CTCAE criteria, the intensity will be assessed by the Investigator as mild (Grade 1), moderate (Grade 2), severe (Grade 3), life-threatening (Grade 4) or death (Grade 5). The Grade 3-4 TEAEs will also be summarized by MedDRA SOC and PT. If a subject experiences the same AE more than once with different toxicity grade, then the event with the highest grade will be tabulated in “by grade” tables. If a subject experiences multiple AEs under the same PT (SOC), then the subject will be counted only once for that PT (SOC).

Analysis of TEAEs of special interest will be presented for combined Phase 1, Phase 2 and the combined Phase 1/2 as described in items 3 to 5 of [Section 5.1](#). Some special interested PTs will be grouped and the TEAEs will be summarized by Grouped Terms and be presented for combined Phase 1/2 as described in item 5 of [Section 5.1](#).

The number of subjects with at least one TEAE will be summarized. Analysis for all TEAEs and Grade 3-4 TEAEs by descending frequency of PT will also be summarized. Tabulations of overall summary of TEAEs, all TEAEs by SOC/PT and Grade 3-4 TEAEs will be summarized by cycles for combined Phase 1, Phase 2, and the combined Phase 1/2. All TEAEs and Treatment-related TEAEs leading to study drug discontinuation, reduction or interruption will be summarized separately. Tables summarizing the incidence of TEAEs will be generated for each of the followings:

1. Overall summary of TEAEs.
2. All TEAEs by SOC and PT.
3. Treatment-related TEAEs by SOC and PT.
4. All TEAEs by descending frequency of PT in total column.
5. All TEAEs with Grade 3-4 by SOC and PT.
6. TEAEs by maximum severity.
7. Treatment-related Grade 3-4 TEAEs by SOC and PT.
8. All TEAE with Grade 3-4 by descending frequency of PT in total column.

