15.1.1. Calculation Using Dates

Calculations using dates (eg, subject's age or relative day after the first dose of study drug) will adhere to the following conventions:

1. Study days after the start day of study drug will be calculated as the difference between the date of interest and the first date of dosing of study drug (eg, lenalidomide) plus 1 day. The generalized calculation algorithm for relative day is the following:
 - If TARGET DATE \geq DSTART then STUDY DAY = (TARGET DATE – DSTART) + 1;
 - Else use STUDY DAY = TARGET DATE – DSTART.

- Note that Study Day 1 is the first day of treatment of study drug. Negative study days are reflective of observations obtained during the baseline/screening period. Note: Partial dates for the first study drug are not imputed in general. All effort should be made to avoid incomplete study drug start dates.
- 2. Age (expressed in days) is calculated: $AGE = \text{CONSENT} - \text{DATE of BIRTH} + 1$. In practice, age will be transformed to years by dividing the difference by 365.25 days, then truncating.
- 3. Preference is for using calculated age from clinical database. When not available, calculated age from eCRF or IVRS may be used
- 4. Partial birth date: impute missing day as 15th of the month; impute missing month as July; set missing age for missing year
- 5. Intervals that are presented in weeks will be transformed from days to weeks by using (without truncation) the following conversion formula:
 - $WEEKS = DAYS / 7$
- 6. Intervals that are presented in months will be transformed from days to months by using (without truncation) the following conversion formula:
 - $MONTHS = DAYS / 30.4$

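### SAP 9.1 credits 27 days of exposure after death when a subject dies on the last dose day, and does not stop exposure at the data cut-off

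*SAP*

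**What the plan says.** SAP 9.1 defines two quantities. Treatment duration counts the days from first to last dose inclusive. Duration of treatment exposure uses the same two dates but adds 28 days instead of 1. Both are divided by 30.4, in line with the conversion in SAP 15.1.1, "MONTHS = DAYS / 30.4".

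In general "the treatment end date is the last dose date". For subjects still on treatment at the cut-off, "treatment end date will be the earlier date of data cut-off date and last day that the subjects take study drug".

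There is one exception to the 28-day addition: "If death date is after treatment end date and earlier than 28 days after treatment end date", exposure instead runs from the treatment start date to the death date inclusive. SAP 9.1 has no clause for a death on the treatment end date and none that ends exposure at the data cut-off. SAP 5.1 says in general that data are analysed "up to the data cut-off date of 29 July 2019".

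SAP 9 summarises exposure in the safety set for all five subject groupings. SAP 9.1 adds a summary by investigator-assessed best response.

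**The concern.** The exception shows that exposure is meant to stop at death. Because it is worded as strictly after the treatment end date, it misses the subject who dies on the day of the last dose, and the default formula then carries that subject past death. The case is a realistic one: dosing is daily and continuous, and SAP 6 lists death among the reasons for stopping treatment.

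The second gap is at the cut-off. The treatment end date of a subject still on drug can be the cut-off date itself, and the 28-day addition then places part of the exposure after the date to which SAP 5.1 limits the analysis.

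A programmer who follows the text literally will reproduce both gaps. At stake is the accuracy of the reported exposure months.

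**Working it through.** The plan states no numerical result for this quantity, so there is no figure to reproduce. The check applies the two SAP 9.1 formulas to dates.

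**Inputs**
- S = treatment start date and E = treatment end date (SAP 9.1)
- D = death date
- C = data cut-off, 29 July 2019 (SAP 5.1)
- 30.4 days per month (SAP 9.1 and 15.1.1)

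**Formulas**
- Default: exposure days = E - S + 28. The last day counted is E + 27.
- Death exception, only if E < D < E + 28: exposure days = D - S + 1. The last day counted is D.

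**Death near the last dose**

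| Treated days | Death on | Rule applied | Exposure days | Months | Days counted after death |
|---|---|---|---|---|---|
| 1-30 | E (day 30) | default | 30 - 1 + 28 = 57 | 1.88 | 27 |
| 1-30 | E + 1 (day 31) | exception | 31 - 1 + 1 = 31 | 1.02 | 0 |
| 1-168 | E (day 168) | default | 168 - 1 + 28 = 195 | 6.41 | 27 |
| 1-168 | E + 1 (day 169) | exception | 169 - 1 + 1 = 169 | 5.56 | 0 |
| day 1 only | E (day 1) | default | 1 - 1 + 28 = 28 | 0.92 | 27 |

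The excess is 27 days whatever the treatment length, and 27/30.4 = 0.89 month. Surviving one day longer lowers recorded exposure by 26 days (57 - 31, or 195 - 169). For deaths from E + 1 to E + 27 the exception ends exposure exactly at death. For deaths at E + 28 or later the default ends before death. Death on E is therefore the only faulty death case.

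**Data cut-off**

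If the last drug day is k days before C, then E = C - k and the last day counted is C - k + 27. The overrun is 27 - k days for k from 0 to 27, unless the death exception applies.

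| k | Last day counted | Days past cut-off |
|---|---|---|
| 0 | 25 August 2019 | 27 |
| 7 | 18 August 2019 | 20 |
| 14 | 11 August 2019 | 13 |
| 26 | 30 July 2019 | 1 |
| 27 | 29 July 2019 | 0 |

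The same arithmetic applies to a subject who stopped drug for good fewer than 27 days before the cut-off.

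**The case against.** The strongest reply is that the formula adds a nominal post-dose window and does not claim that every day in it was observed. On that view the missing cut-off cap is untidy rather than wrong, since SAP 5.1 already limits the data. This has some force for the cut-off, which is the weaker of the two gaps. It does not answer the death case, because the SAP's own exception ends exposure at death and fails on one date only.

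It is also fair to say that little depends on the quantity. Dose intensity (SAP 9.4) divides by treatment duration, relative dose intensity (SAP 9.5) follows from it, and the primary endpoint (SAP 10.2) does not use exposure. Treatment duration, without the added window, is reported alongside. SAP 11.1 reports adverse events as subject incidence, not as exposure-adjusted rates. This stands and limits the importance of the point.

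A reader might infer more than the documents support:
- **That the window is a day short of the adverse-event window.** SAP 11.1 counts events "on or after the start of study drug through 28 days after the last dose of study drug", whereas exposure ends at E + 27. Neither section refers to the other, and nothing requires the two to match. A 28-day window that includes the last dose day is coherent.
- **That the by-response table is biased towards responders.** This assumes that subjects on drug at the cut-off are mostly responders. The documents give no such figures, and Protocol 10.8.3 allows subjects with stable or progressive disease to continue.
- **That every subject on drug at the cut-off gains 27 days.** That is the maximum, reached when the last drug day is the cut-off date.
- **That the 56-day transfusion independence rate is inflated.** SAP 4.2.1 and 10.3.1.6 assess it over a treatment exposure period but do not tie that period to the SAP 9.1 formula, so the link would be an assumption.

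**Conclusion.** The point holds, as a wording gap in a derivation. Read literally, SAP 9.1 credits a subject who dies on the last dose day with 27 days (0.89 month) after death, and credits subjects whose last drug day is k days before the cut-off with up to 27 - k days beyond it. The first is a clear fault against the SAP's evident intent; the second is a missing cap.

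The sizes per subject are exact and assume only that the text is programmed as written. The total effect cannot be stated, because the documents give neither the number of deaths on the last dose day nor the number of subjects with a last drug day fewer than 27 days before 29 July 2019. The consequence is confined to the descriptive exposure summaries, including those by best response. It is a minor correction.

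**What to change.** Replace the formula and its exception in SAP 9.1 with two definitions:
- Exposure end = earliest of treatment end date + 27 days, death date, and data cut-off date.
- Duration of treatment exposure (months) = (exposure end - first dose date + 1)/30.4.

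For the subject treated on days 1 to 30 who dies on day 30, this gives 30 days instead of 57; death on day 31 still gives 31. A subject treated for 168 days whose last drug day is the cut-off gets 168 days instead of 195. Where neither death nor the cut-off intervenes, exposure is (E + 27) - S + 1 = E - S + 28, exactly as now.

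The 27 matters. Using last dose + 28 days with the same inclusive count would give E - S + 29 and add a day for every subject not limited by death or the cut-off.

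The cost is one line of SAP text, one changed derivation and a rerun of the exposure summaries. No new data are needed, and exposure becomes shorter only for the affected subjects.

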9.2. Cumulative Dose

Cumulative dose is defined as the sum of all doses taken during the treatment period in mg.

9.3. Average Daily Dose

Average daily dose is defined as the cumulative dose divided by number of days dosed. A single average value will be computed for each subject, and then the descriptive statistics (number of subjects, mean, SD, median, minimum and maximum) will be computed for each subject group.

9.4. Dose Intensity

Dose intensity during the treatment is defined as the cumulative dose divided by the treatment duration. The descriptive statistics (number of subjects, mean, SD, median, minimum and maximum) will be computed for each subject group.

Dose intensity for AG-221 = $[\text{cumulative dose for AG-221 in mg}] / [\text{treatment duration in days}]$.

9.5. Relative Dose Intensity

Relative dose intensity is the actual dose intensity as defined in the previous section divided by the planned dose intensity. The planned dose intensity is based on initially assigned daily dose.

Relative dose intensity for AG-221 will also be categorized into <75%, 75% to <90%, 90% to <120%, and \geq 120%. The descriptive statistics and frequency counts will be provided by subject group.

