
Investigational product, dosage and mode of administration: AG-221 (AG-221 mesylate) will be provided as 5, 10, 25, 50, 100, 150 and 200 mg free-base equivalent strength tablets to be administered orally.
 
Phase 1/Dose Escalation The first 3 subjects in each cohort in the dose escalation portion of the study and the first 15 subjects in each arm of Part 1 Expansion will receive a single dose of study drug on Day -3; their next dose of study drug will be administered on C1D1 at which time subjects will start daily dosing on Days 1 to 28 in 28-day cycles. Starting with C1D1, dosing is continuous; there are no inter-cycle rest periods. Subjects who are not required to undergo the Day -3 PK/PD assessments will initiate daily dosing with AG-221 on C1D1.
 
The dose of AG-221 administered to a subject will be dependent upon which dose cohort is open for enrollment when the subject qualifies for the study. The starting dose of AG-221 to be administered

Name of Sponsor/Company: Celgene Corporation
Name of Investigational Product: AG-221
Name of Active Ingredient: AG-221 mesylate
to the first cohort of subjects is 30 mg administered orally twice a day, and the maximum administered dose of AG-221 to be administered is 650 mg administered orally once a day. Phase 1/Part 1 Expansion and Phase 2 The starting dose of AG-221 recommended for evaluation is 100 mg QD. This is based on the safety, PK, pharmacodynamics and clinical activity of AG-221 observed to date in AG221-C-001. Evaluation of pharmacodynamic response demonstrated sustained reduction in 2-HG plasma levels by Day 1 of Cycle 2 and up to 98% inhibition in most subjects with R140Q mutation at all doses. Increasing dose is associated with higher exposure and inhibition of 2-HG in subjects with R172K mutation. Importantly, preliminary efficacy data of the 44 subjects treated at 100 mg QD has shown an overall response rate of 36.4%. Thus a dose of 100 mg should adequately achieve inhibition of 2-HG in subjects with either R140Q or R172K mutation. Moreover, the safety profile at 100 mg, including $\geq$ Grade 3, is consistent with that of lower doses. Intra-subject dose escalation is possible as per criteria in Section 9.7.2.1 .

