### 10.6.2. Vital Signs

Vital signs, including systolic and diastolic BP, heart rate, respiratory rate, and temperature, will be obtained at screening, on Day 15 of Cycle 1, on Day 1 of every treatment cycle through at least Cycle 12, and every 3 cycles thereafter, and at the End of Treatment visit. Assessments should be conducted while the subject is seated or supine.

Additionally, serial vital signs are to be obtained following the first dose of study treatment (i.e., on Day -3 for subjects undergoing the 72-hour PK/PD profile or on C1D1 for subjects who do not attend the Day -3 assessment) at the following times: predose, and 30 ± 10 minutes and 2, 4, 6, and 8 hours (± 15 minutes) post dose following the morning administration of study drug. Note that subjects should be instructed to take their dose of AG-221 in clinic on these days.

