- Data from all study centers will be combined in the analysis.
- P-values will be rounded to 4 decimal places. P-values that round to 0.0000 will be presented as '<0.0001' and p-values that round to 1.000 will be presented as '>0.9999.'
- Confidence intervals (CIs) will be presented as 2-sided 95% CIs unless otherwise specified.
- Summary statistics will consist of the number and percentage of subjects in each category for discrete variables, and the sample size, mean, median, SD, minimum, and maximum for continuous variables.
- All percentages will be rounded to one decimal place. The number and percentage of responses will be presented in the form 'xx (xx.x)', where the percentage is in the parentheses.
- All analyses and summary tables will have the analysis population sample size for each treatment group in the column heading (ie, number of subjects).
- The day of the first dose of the study drug will be defined as study Day 1.
- For all analyses, unless noted otherwise, baseline will be defined as the most recent non-missing measurement by the first administration of study treatment. For subjects who receive the single dose on Day -3, baseline will be defined as the most recent measurement by the dosing on Day -3. For subjects who do not receive the single dose on Day -3, baseline will be defined as the most recent non-missing measurement by the first dose date.
- To summarize efficacy/safety data by visit, the post-baseline results will be summarized by the scheduled visit as appropriate.
- Calculation of Cycles:
 - The start date of each cycle will be determined based on scheduled study visit date for each subject, except for Cycle 1 which will use the first dose date of study drug as starting day. Once the start dates, eg, $S_1, S_2, S_3 \dots$ are determined, the end date of each cycle is calculated as the one day before the start date of the following cycle, ie, $E_i = S_{i+1} - 1$. The cycle number for each date of interest, eg, AE or study medication will be calculated based on event start date and the cycle window start and end dates. If an event date is on or after S_i and before S_{i+1} , the corresponding cycle number will be i . For the last cycle, the end date will be the last dose date, unless otherwise specified.

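### For Phase 1 subjects given the Day -3 PK dose, relative dose intensity counts two planned no-dose days as days of expected full dosing, so adherent subjects who stop early fall into the lower bands

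*SAP*

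**What the plan says.** Four SAP definitions combine.

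- Duration (SAP 9.1): "The treatment start date is the date of the first dose of study drug, and the treatment end date is the last dose date". In days this is end minus start plus 1.
- Cumulative dose (SAP 9.2): "Cumulative dose is defined as the sum of all doses taken during the treatment period in mg". The Day -3 dose is therefore included.
- Dose intensity (SAP 9.4): "Dose intensity during the treatment is defined as the cumulative dose divided by the treatment duration".
- Relative dose intensity (SAP 9.5): actual over planned dose intensity, where "The planned dose intensity is based on initially assigned daily dose". The result is also tabulated as <75%, 75% to <90%, 90% to <120% and at least 120%.

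The Protocol Synopsis (Phase 1/Dose Escalation) says that the first 3 subjects in each escalation cohort and the first 15 in each Part 1 Expansion arm "will receive a single dose of study drug on Day -3; their next dose of study drug will be administered on C1D1". Protocol 7.1.4 puts the 24-, 48- and 72-hour samples on Days -2, -1 and 1, so there is no Day 0 and two calendar days pass without a dose.

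Both documents treat Day -3 as the first dose. Protocol 10.6.2 schedules serial vital signs "following the first dose of study treatment (i.e., on Day -3 for subjects undergoing the 72-hour PK/PD profile". SAP 5.1 states: "For subjects who receive the single dose on Day -3, baseline will be defined as the most recent measurement by the dosing on Day -3". The SAP thus has a lead-in rule for baseline, but SAP 9.1 to 9.5 contain none.

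**The concern.** The duration includes two days on which the protocol plans no drug, while the planned intensity assumes the full daily dose on every day. A scheduled PK procedure is therefore scored as missed dosing.

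The shift is largest in subjects treated for a short time. The fixed bands turn it into counts of subjects in the wrong category, not only a slightly lower mean. SAP 9 also asks for these tables by assigned dose in the Dose Determining Set, and SAP 5.2.3 admits subjects with a DLT to that set whatever their exposure, so early stoppers are included.

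Phase 2 has no Day -3 dose (Protocol 7.1.4). In the combined Phase 1/2 tables (SAP 5.1, item 5) the dose columns can therefore carry unequal shares of the artefact.

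**Working it through.** The documents give no value of relative dose intensity (RDI), so there is no figure of theirs to reproduce. The check applies the SAP definitions to a fully adherent subject.

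**Inputs.** D is the initially assigned daily dose (SAP 9.5). n is the number of consecutive full daily doses from C1D1, at least 1. The subject took the Day -3 dose and had no dose increase.

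**Duration (SAP 9.1).** Days -3, -2 and -1 plus Days 1 to n: n + 3 days.

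**Once daily (QD), with the Day -3 dose equal to D.** Cumulative dose is (n + 1) × D, so RDI = [(n + 1)D / (n + 3)] / D = (n + 1)/(n + 3).

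| n | RDI | Band |
|---|---|---|
| 4 | 5/7 = 71.4% | <75% |
| 5 | 6/8 = 75.0% | 75 to <90% |
| 14 | 15/17 = 88.2% | 75 to <90% |
| 16 | 17/19 = 89.5% | 75 to <90% |
| 17 | 18/20 = 90.0% | 90 to <120% |
| 28 | 29/31 = 93.5% | 90 to <120% |
| 98 | 99/101 = 98.0% | 90 to <120% |
| 168 | 169/171 = 98.8% | 90 to <120% |

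The shortfall is 2/(n + 3). It equals 2 points at n = 97 and is below 2 points from n = 98, which is 98/28 = 3.5 cycles.

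**Subjects who complete Cycle 1 with real missed doses.** A QD subject last dosed on C1D28 with 2 doses missed in between scores (1 + 26)/31 = 87.1% under the SAP. Against the planned doses, 1 + 28 = 29, the same subject scores 27/29 = 93.1%. The band changes.

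**Twice daily (BID).** The documents say only that a single dose is given on Day -3.
- If it equals the full daily dose, the QD values apply.
- If it is one of the two daily doses (an assumption), RDI = (n + 0.5)/(n + 3). That is <75% for n = 1 to 6, 75 to <90% for n = 7 to 21, 90.0% at n = 22, and 28.5/31 = 91.9% at n = 28.

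**Subjects with the lead-in, by plan.** 13 dose levels/schedules × 3 + 4 arms × 15 = 39 + 60 = 99. The minimum Phase 1 size in SAP 4.4 is 12 × 5 + 6 + 100 = 166.

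**Limits of the formula.**
- A subject who took only the Day -3 dose has a duration of 1 day and, on QD, an RDI of 100%.
- A QD subject raised from 100 to 200 mg after 2 cycles who stops after cycle 3 has (1 + 56 + 2 × 28)/(84 + 3) = 113/87 = 129.9%.

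**The case against.** The strongest reply is that little hangs on this. RDI is one of several descriptive exposure summaries in SAP 9. Average daily dose (SAP 9.3) divides by days dosed, so an adherent QD subject scores exactly D, and SAP 9.6 reports reductions and interruptions directly. The MTD rests on DLTs in the Dose Determining Set, whose 75% rule counts planned Cycle 1 doses and not RDI. All of this stands, and it limits the point to the quality of one table.

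It can also be said that the wording in SAP 9.5 is loose enough for a programmer to allow for the lead-in. That is fair, but no such rule is written. Two programmers could produce different tables, and the literal reading gives the values above.

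A reader might infer more than the documents support:

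- *That no adherent Phase 1 subject can reach 100%.* The shortfall applies only to those who took the Day -3 dose, continued to C1D1 and had no dose increase. Protocol 9.7.2.1 allows increases.
- *That early stoppers are classed as under-dosed.* SAP 9.5 has numeric bands without labels, and no decision is attached to them.
- *That 99 of 166, about 60%, are misclassified.* The 166 is a minimum. The Medical Monitor may omit the lead-in (Protocol Table 2, footnote 1) or require it beyond the first 15 per arm (Protocol 10.9.1). A wrong band for an adherent QD subject also needs a last dose between C1D1 and C1D16, and the documents give no estimate of how many stop that early.
- *That Phase 1 is shown at a disadvantage to Phase 2.* The combined tables pool subjects by total daily dose and malignancy type; they do not set the phases against each other.

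**Conclusion.** The point holds on the literal reading of SAP 9.1, 9.4 and 9.5, for Phase 1 subjects who took the Day -3 dose and had no later dose increase. Two planned no-dose days enter the denominator as days of expected full dosing. On QD, a fully adherent subject is banded too low when the last dose falls between C1D1 and C1D16. At one full cycle the figure is 6.5 points low but the band is right, and at six cycles the bias is about 1 point (2/171 = 1.2).

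The QD figures assume that the Day -3 dose equals the assigned daily dose. BID values are lower only if that dose is half the daily dose, which the documents do not state. About 99 planned lead-in subjects is neither a maximum nor a count of wrong bands.

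This is a minor correction to a descriptive exposure summary. No efficacy endpoint, safety criterion or MTD decision depends on it.

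**What to change.** In SAP 9.5, define planned cumulative dose as the planned Day -3 single dose (if given) plus the initially assigned daily dose times the number of days from C1D1 to last dose, inclusive, with zero days if dosing ended before C1D1. Define RDI as actual cumulative dose divided by planned cumulative dose. Leave SAP 9.1, 9.2 and 9.4 unchanged.

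A fully adherent subject then scores 100% for every n, on QD or BID, whatever the size of the Day -3 dose. A subject who took only that dose also scores 100%.

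Starting the clock at C1D1 and ignoring the Day -3 dose may look like a simpler equivalent, but it should not be offered as an alternative. With 9 days from C1D1 to last dose and one missed QD dose, the definition above gives (1 + 8)/(1 + 9) = 90.0%, whereas the C1D1 clock gives 8/9 = 88.9%, which is a different band. The C1D1 clock is also undefined for a subject who took only the Day -3 dose.

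The cost is one sentence and a changed derivation from dates already collected. There is a small downside. For lead-in subjects, RDI will no longer equal the reported dose intensity divided by the assigned daily dose, and it may differ from outputs at the earlier cut-offs listed in SAP 12. A table footnote should say so.
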